Educational attainment	X		
Health literacy –S-TOFHLA, ANQ, eHealth Literacy	X		
Comorbidities	X		
Depressive thoughts	X		
Primary language	X		

*Quarterly data collection occurs at months 3, 6, 9, and 12 and every 3 months after month 12 until the end of the study.

** We collect outcomes quarterly, at 12 months, and every 3 months until the study ends. Final visit is the final visit of data collection that occurs after the 12-month collection.

+Prednisone bursts are defined as a new prescription or an increase in dose of prednisone.

++FEV1 could be collected for only 203 patients owing to non-availability of spirometry equipment at the start of the study.

#The Inhaler Adherence Scale asks participant's report of non-adherence.^{29,30} It is a 6-item scale with each item scored 1 (non-adherence) or 0 (adherence). The range is 0-6, with 0 being optimal adherence.

Time frame for the study

All participants were to be followed for data collection every 3 months for at least 1 year (please see the Home Visitor Protocol sub-section and Figure 1). We chose a 3-month interval for data collection, as the Expert Panel Report uses 3 months for making a change such as “stepping down.”³¹ We chose the times for home visits, based on [name] experience with home visits in children. She found it was important to have home visits early in participation.³² We wanted the last 6 months to be for observation to assess sustainability. For reasons for withdrawals or becoming lost to follow-up, please see Figure 2.

Data collection and sources

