Irregular data collection times (see results) required models that used outcome time as a continuous measure. For that reason, analysis models implemented spline based marginal (GEE) (MCAR assumption) and mixed effects (MAR assumption) longitudinal models, both identity/Gaussian, log/Poisson, and log/gamma with marginal splines to estimate expected values of outcomes at 0 months and 12 months and outcome changes between 0 and 12 months. We used all data collection times and the actual times. We did not artificially categorize data collection times to equate to the preplanned 0, 12, 24, 36, and 48 weeks from randomization. The contrast (estimator) of interest was the difference between the treatment groups in the changes in expected values from 0 months to 12 months. Examples in the statistical literature support this approach.⁴⁵ All confidence bounds were estimated using 999 bootstrap resamples (percentile-based). By using 999 samples, confidence bounds are from the 25th and 975th order statistics without interpolation. Details appear in Appendix A7.

Model form

We used both marginal and mixed effects models, with the marginal model being the primary approach owing to convergence problems with mixed effect models (noted below).⁴⁶ By including splines for time and group-by-time interaction terms, these models could produce the expected values at 0 and 12 months and predicted values of interest.

For the primary outcome of asthma control, the skewed distribution of outcomes necessitated that we use log gamma models. The treating clinic was a stratifying factor in all models to account for the stratified randomization.

Alternative approaches for estimating asthma control

Differences between intervention groups in expected values at given follow up times, although statistically appropriate for comparing groups, lacks an immediate connection to the manner in which clinicians might want to interpret results. For that reason, we pre-planned two methods for translating findings into clinically useful metrics.

(1) Fraction of patients who have achieved asthma control (a level below 1.5 on the scale):

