We avoided dichotomizing data, an ad hoc approach, but instead used mixed effects linear model and predictions to report the change in the fraction of patients who achieved adequate control. This prediction accounts for patient variation about the expected value and in theory represents a better estimate of the patient's true outcome (asthma control) than does the patient's observed value. Once we estimated each patient's predictions at baseline and at 12 months, we dichotomized these model-based predicted values to estimate the fraction of patients who achieved asthma control at baseline and at 12 months in each group. This is not the primary analysis, however, but represents an alternative demonstration of intervention effectiveness. Details appear in Appendix A8.

(2) Minimally important improvement: For estimates of the improvements at the patient level on the asthma control (Juniper) scale, the minimally important difference is 0.5.^{23,47} Again, the model-based predicted values are the best estimates at the individual level of the level of asthma control at a given time and account for measurement error as well as variation across individual patients. We compared changes in individual predictions of asthma control at 0

months and 12 months and counted the number of predictions that improved by at least 0.5. Methodological details appear in Appendix A8.

Sensitivity analyses

We planned the following sensitivity analyses, and pre-specified the endpoint for these analyses to be the between- group differences of the change over time of asthma control from baseline to 12 months.

Sensitivity analysis #1. Selection bias from loss to follow-up – covariate adjustment

In keeping with recommendations,^{48,49} we included in our longitudinal analysis model (described previously), in addition to the randomized treatment assignment and the pre-planned stratification variable (clinical site), the covariates that might be related to dropout and the primary outcome. Appendix A9.

Sensitivity Analysis #2. Nonignorable timing of data collection -- Global sensitivity analysis to irregular visit times and dropout

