Typically reports of longitudinal studies use time as a categorical factor. When all patients are measured at the same time, this analytic approach is entirely appropriate. For such studies as ours, however, this approach was both not feasible and theoretically unsound. For that reason we modeled actual data collection times using a flexible approach – marginal splines.

As with many studies, and in particular as with studies that involve mostly disadvantaged patients who also have underlying comorbidities that limit their mobility, contact and meeting availability with research personnel for the preplanned data collection times, this difficulty presents challenges. The preplanned times were 0, 12, 24, 36, and 48 weeks from randomization. But patients could not be contacted and interviewed at these times due to the previously mentioned challenges. This reality led to measurements at times that differed from, but mostly followed, the preplanned times. With irregular data collection times, we therefore used the following method of analysis.

Methods for irregular data collection times

- (1) For analysis, we used all data whenever obtained. No interviews were considered to be out of range. We used all interviews even for those patients who dropped out after baseline interviews but before the completion of the fifth and final interview.
- (2) Unlike many studies, we modeled time as a continuous measure rather than as a categorical factor. We recorded and used for each patient the actual time (months from randomization) of the interview.
- (3) With continuous time, we needed then to allow for non-linear trajectories of outcomes over time. We made no assumptions about linear trends in health improvement arising out of the

Appendix A7 (continued). Methods for handling Irregular data collection interviews - Unified modeling approach.

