Mixed effects models that include random effects to represent individual patient departures from average levels of outcomes, such as asthma control, have long been used to address these issues of measurement error. The resulting "predictions" of individual levels of outcomes are in theory better, less biased, estimates of individual-level outcomes that are the raw observations. (Efron; Morris; Casella). In this application, we implemented longitudinal models with two different types of random effects. Random intercepts reflect the individual departure of outcomes (asthma control) at baseline, in our case at randomization (month 0). Random slopes reflect the departure of individual level trajectories from the average trajectory of change in outcomes over time. With these two types of random effects, we could predict each patient's level of outcome at two common times: the date of randomization and 12 months later. We used these predictions, and their differences, of asthma control to estimate the number of patients who were in control (score <1.5) and who had achieved a clinically important reduction in score (decrease of 0.5), which reflects an improvement in asthma control.

We used restricted maximum likelihood (REML) as implemented in the program "mixed" in Stata version 15.1 to fit a linear mixed model. Our attempts to fit generalized linear mixed models, such as a log gamma model with log link and gamma error, all failed to achieve convergence. Thus, this linear model did not fully reflect the skewed nature of the data but represented the best alternative.

In our application, defining and implementing random slopes became more complex because of our use of splines to estimate the changes over time in outcomes (See main text for description of the primary analysis). The time line of observation was divided into segments, with each segment allowed to have a different slope (or trajectory) of the outcome over time. We began with a model that had the same set of 5 line segments for time as did the primary model. We then added all of the baseline covariates (as in the primary analysis) in order to explain as much as possible the individual patient-level variation in outcome. To this model, we added a random intercept for each patient and a single random slope to reflect overall

Appendix A8 (continued). Fitting mixed effects models to estimate individual improvement in asthma control and achievement of asthma control.

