departure of the individual over time from the average trajectory not explained by these observed covariates. The model converged. We then added a second random slope to represent an additional element of individual patient departure from average as the follow-up time progressed. This model converged in 10 iterations. Models with additional random slopes to reflect the additional time segments of the spline model would not converge.

The final model, included as fixed effects: Linear (marginal) spline with knots at 3,6, 9, and 12 months; clinic, Spanish as the primary language, age categorized (18-39, 40-49, and 50+), literacy levels (4 levels from latent class models), social support(3 levels from latent class models), smoking exposure(4 –levels: none, first hand smoke only, second hand smoke only, both first and second hand smoke), comorbidities (3-level latent class model: healthy, depressed, other chronic comorbidities), baseline asthma severity (low high), concern about using health data on the internet (5 levels), home crowding (3 levels: <1 per room, 1 up to 2 per room, 2+ per room).

Random effects included: a random intercept for subject and a random slope for the first two line segments constructed by the spline model.

This analysis can best be thought of as a sensitivity analysis to the main findings of the asthma control outcome. Its limitations are that there were insufficient data to fit a log-link, gamma-family model with more than 2 random slopes.

References

2. Morris CN. Parametric empirical Bayes inference: Theory and applications. J. Amer. Statist. Assoc. 1983;78:47–65. with discussion.
3. Casella G. An introduction to empirical Bayes data analysis. Amer. Statist. 1985;39:83–87.

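### Counting shrunken predictions that pass 0.5 does not estimate the share of patients who improved by 0.5

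*Combined protocol and SAP*

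**What the plan says.** Under Alternative approaches for estimating asthma control, the main text plans two translations of the primary result for clinicians. Item (2) takes its threshold from the scale ("the minimally important difference is 0.5"), compares each patient's model predictions at 0 and 12 months, and "counted the number of predictions that improved by at least 0.5". The reason given is that "the model-based predicted values are the best estimates at the individual level of the level of asthma control at a given time". Appendix A8 (Methods) uses the predictions and their differences "to estimate the number of patients who were in control (score <1.5) and who had achieved a clinically important reduction in score".

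The model is a linear mixed model fitted by REML, chosen because log-gamma mixed models did not converge. It has a random intercept and random slopes for the first two spline segments. Two features of it are unclear:

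- **Treatment arm.** Model form in the main text says of the marginal and mixed models: "By including splines for time and group-by-time interaction terms, these models could produce the expected values at 0 and 12 months". Appendix A8's itemised list starts "The final model, included as fixed effects: Linear (marginal) spline with knots at 3,6, 9, and 12 months; clinic" and continues through baseline covariates, with no arm or arm-by-time term.
- **Interviews per patient.** The Table 2 footnote has quarterly collection "every 3 months after month 12 until the end of the study". Appendix A7 speaks of patients who left "before the completion of the fifth and final interview".

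Appendix A8 names skewness and the limit of two random slopes as its limitations. It does not mention what shrinkage does to a count.

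**The concern.** Appendix A8 opens by noting that group means cannot show whether everyone improved or some improved while others worsened. The target is therefore the distribution of individual change. A prediction can have the smallest squared error for each patient while the set of predictions has too little spread, and a count past a cut-off depends on the spread. Each arm's predictions are pulled towards that arm's mean change (or towards one common trajectory, if arm is not in the model), and patients cross 0.5 in the wrong numbers.

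Clinicians will read this metric as the share of patients with an important improvement. Both arm shares and their difference can be off, in either direction. Bootstrap percentile bounds resample the same statistic and do not remove the error.

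**Working it through.** **1. What the plan supplies.** It states no responder share, so there is none to reproduce. The one design figure that can be rebuilt is power: 150 per arm, a difference of 1/3 SD and two-sided 5% (my assumption) give 0.823, matching the lower end of the stated 0.82 to 0.87. That says nothing about individual change. The remark that 1/3 SD is below 0.5 implies only that the score's SD is below 1.5. Everything below therefore uses assumed values.

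**2. Formula.** Let D be the fall in score from 0 to 12 months, with mean μ and SD τ in an arm. The covariates listed in Appendix A8 have no time interactions, so they cancel from D. Within an arm, the spread of predicted D then comes only from the two random slopes. With independent slopes on t and (t−3)+, τ² = 12²σ₁² + 9²σ₂². For data Y,

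Var(E[D|Y]) = Var(D) − E[Var(D|Y)] = Lτ², with L < 1.

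Under normality:

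- true share = Φ((μ − 0.5)/τ)
- counted share = Φ((μ − 0.5)/(τ√L))

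These agree only if L = 1 or μ = 0.5 exactly. Slope SDs of 0.05 and 0.03, for example, give τ² = 144×0.0025 + 81×0.0009 = 0.433, so τ = 0.66. For τ from 0.66 to 1.06 and residual SD 0.5 to 0.9, L was 0.36 to 0.80 with five visits and 0.14 to 0.52 with three.

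**3. One arm** (τ = 0.8, L = 0.5, √L = 0.707).

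- μ = 0.2: true Φ(−0.375) = 35.4%; counted Φ(−0.530) = 29.8%.
- μ = 0.5: 50% both ways.
- μ = 0.8: true 64.6%; counted 70.2%.

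Over τ 0.6 to 1.0, μ 0 to 1.0 and L 0.3 to 0.9, the error runs from about −14 to +14 points.

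**4. Two arms, arm terms fitted.** Assumed: intercept SD 0.9, residual SD 0.7, baseline 2.3, mean improvements 0.3 (PT) and 0.6 (PT+HV), delayed visits. Ratio = counted difference / true difference, from unrounded shares.

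| τ | True PT / PT+HV | Counted, 5 visits | Ratio, 5 visits | Ratio, 7 visits |
|---|---|---|---|---|
| 0.4 | 31 / 60% | 13 / 71% | 2.0 | 1.47 |
| 0.6 | 37 / 57% | 29 / 61% | 1.64 | 1.26 |
| 0.8 | 40 / 55% | 36 / 57% | 1.41 | 1.16 |
| 1.0 | 42 / 54% | 40 / 55% | 1.28 | 1.10 |

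The direction can reverse. With mean improvements 0.8 and 1.0, τ = 0.4 and five visits, true 77/89% is counted as 95/100%, a ratio of 0.35.

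**5. Grid.** Four values of τ × six mean pairs × three residual SDs × three splits of slope variance = 216 settings, arm terms fitted.

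- Five visits: median ratio 1.32 (10th to 90th percentile 1.06 to 1.70, extremes 0.18 to 2.53); median of the larger single-arm error 7 points.
- Seven visits: median 1.14 (1.05 to 1.33, extremes 0.63 to 1.76); 3 points.

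**6. No arm terms.** Every setting understates the difference: median ratio 0.60 (five visits) and 0.55 (seven). A separate simulation with mean improvements 0.3 and 0.7 and residual SD 0.7 gave a true difference of 18.9 points, 27.0 counted with arm-by-time terms and 13.0 without.

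**7. REML fits at n = 301**, difference in points. Averaged means the mean within arm of each patient's conditional probability of improving by at least 0.5.

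| Setting | True | Counted | Averaged |
|---|---|---|---|
| τ 0.6, 5 visits, arm terms | 19 | 33 | 20 |
| τ 1.0, 5 visits, arm terms | 13.5 | 17.4 | 13.4 |
| τ 0.6, 7 visits, arm terms | 19.0 | 22.7 | 18.7 |
| τ 0.6, 5 visits, no arm terms | 20 | 12 | 7 |

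In the first row, the SD of the difference across replicates was 19 points counted and 11 averaged. With gamma (shape 2) random effects and residuals, τ 0.6 and five visits, shares were true 43/63%, counted 33/63%, averaged 39/57%.

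**8. Score below 1.5.** With arm terms and the step 4 type of inputs, the 12-month share is within 2.5 points in each arm and the difference within 1.4. At baseline the counted share was about 2 points low, and 3.5 points low with intercept SD 0.6.

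**The case against.** The main text and Appendix A8 present this as a re-expression or sensitivity analysis, and the primary GEE contrast does not depend on it. That stands, and it limits the weight of the point.

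The sizes rest on assumed inputs, and the step 4 means straddle 0.5, which favours inflation. This also stands. With τ 0.8 and five visits, mean improvements of 0.4 and 0.5 give true 45/50% against counted 43/50%, and with seven visits errors can be small. But the bias itself needs no assumed value, only its size does.

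Counting raw changes would be no better: measurement error widens their spread and biases the share the other way (τ 0.8, μ 0.2, reliability 0.5: 39.5% against a true 35.4%). True, and raw counts are not proposed.

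The plan says the scores are heavily skewed. In the skewed check, absolute arm errors total 10 points for counting (10 + 0) and 10 for averaging (4 + 6). So under strong skew the remedy clearly improves the difference (true 20, counted 30, averaged 18) but not the arm shares overall.

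The missing arm terms are probably an incomplete list, since Model form and Appendix A7 describe group-by-time terms for both model types. That is the likelier reading. It still needs confirming, because it decides which way the difference is usually distorted.

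**Conclusion.** The concern holds. Except at perfect reliability, or at an arm mean improvement of exactly 0.5 under symmetry, the count does not estimate the responder share, and nothing in the plan corrects or discloses this. With arm terms fitted, the between-arm difference is usually overstated when the arm means lie near or either side of 0.5, and can be understated when both lie well to one side. Without arm terms it was understated in every setting tried.

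The size is illustrative: it depends on variance components, mean changes and visits per patient that the documents do not give. The fraction with a score below 1.5 is little affected at 12 months when arm terms are present, and somewhat more at baseline. This should be corrected, but it is a secondary metric and the primary result stands as planned.

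**What to change.** Keep the Appendix A8 linear mixed model and change what is done after the fit.

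1. Reconcile Appendix A8 with Model form by stating that arm and arm-by-spline terms are fixed effects. This is a precondition: without them, averaging does worse than counting (7 against 12 points, true 20).
2. For each patient take the conditional mean mᵢ and variance vᵢ of the improvement, or draws from the random effects, and compute pᵢ = Φ((mᵢ − 0.5)/√vᵢ). Average pᵢ within arm and take the difference. If the model holds, the expectation of this average is the true share.
3. Do the same for the score below 1.5 at 0 and 12 months.
4. Use the same 999-resample patient-level percentile bootstrap, refitting each time.
5. Report an estimated share, not a number of patients. Because Appendix A8 already describes completed fits, label the change as made afterwards and show the planned count beside it.

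The cost is a short block of code, a bootstrap rerun and a few sentences of text. The method relies on the normal random effects that the model already assumes. With strong skew, arm shares were 4 to 6 points low and the difference was within 2 points of the truth, and the text should say so.

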Appendix A: Additional description of data analyses and accompanying tables.

Appendix A1. PCORI Visit Schedule and list of case report forms used in REDCap.

PCORI Visit Schedule

Visit form	PP2	V1 baseline	V2 week 12	V3 week 24	V4 week 36	V5 week 48	Home Visits			
							A	B	C	D
Asthma Control (ACON)/ Spanish		X	X	X	X	X				
Adverse Events and Serious Adverse Events (AE)			X	X	X	X				
Asthma History (AST)/Spanish		X								
Center for Epidemiologic Studies Depression Scale (CESD)/Spanish		X								
Concomitant Medication (CMED)		X	X	X	X	X				
General Information (GEN)/Spanish		X								
Eligibility (Inclusion/Exclusion) Worksheet (ELIG)		X								
Numeracy (NUM)/Spanish		X								
MOS Social Support Survey Questionnaire (MOS)/Spanish		X								
Randomization (RAND)		X								
Quality of Life (QOL)/Spanish		X	X	X	X	X				
STOFHLA (STOFHLA)/Spanish (administrative)		X								
STOFHLA Score (SCORE)		X								
Spirometry (SPIR)		X				X				
Study Stop (SSTOP)						X				
Inhaler Techniques - MDI (MDI)		X								
Smoke History (SMOKHX)		X								
Standard Visit (STV)/Spanish		X	X	X	X	X				
Inhaler Adherence Scale (INH)/Spanish		X	X	X	X	X				
E-Health Literacy Scale (HLS)/Spanish*		X				X				
Contact Information (CONTACT) (administrative)		X					X	X	X	X
Patient Portal Training 2 (PT2)	X	X								
Patient Portal Training 1 (PT1) (administrative)		X								
Home Questionnaire (HOME)		X								
Home Needs Assessment (HVISIT)							X			
Asthma Care Coordination Goals (GOALS)							X			
Asthma Action Plan (administrative)							X			
Report to Clinician (REPORT)							X	X	X	X
Portal Use Baseline Survey (PORTAL)		X								
Information Technology Survey (INFOTECH)		X								

Appendix A2. Patient portal in EPIC - Data management details.

The Patient Portal in the Epic electronic health record represents an administrative database that underlies the functioning of the patient portal. To our knowledge it has not previously been used for research purposes similar to those we describe in this report. For that reason, we had to devise an approach to capture these raw data and transform them into information for research purposes.

We first had to determine the correspondence among the items in the Portal menu that the patient typically sees on a computer or iPad or smart phone, the selection of these items, and the data records ultimately stored in the underlying database. To understand the Portal process, we established a simple protocol of menu items to select in a given order and at preset times. Then one investigator ([name]), using his own patient Portal account and this protocol, systemically executed each step with pre-specified time delays (in seconds) between each menu selection. The investigator repeated this process for both the EPIC Portal designed for the personal computer, and the EPIC Portal designed for the iPad and smartphone. Then, we notified the investigator who had access to the Portal database ([name]) to retrieve the database transactions. Finally, we compared the protocol-based menu selection with the resulting data entries to identify what menu selection result in different recorded activities.

The Clarity database is a large subset of data that comes from the PennChart (Epic) application. The Portal data from the University of Pennsylvania system entered the PennChart Chronicles dataset. We transferred the Portal data from the PennChart Chronicles database to Clarity, a Microsoft SQL Server database comprised of over 18,000 tables. After several trials, the “MS data only” option seemed to work best in Crystal Reports in creating a smaller report that can be used as data for analysis.

A special challenge with these types of data arises when the medical record number, which ideally should remain unchanged, does in fact change during the course of the study. Although our study followed patients for a limited time (almost all patients for less than 2 years), we found that medical record numbers did change, and communications with the information technology departments requested multiple searches of data for individual patients.

